10.0 STATISTICAL CONSIDERATIONS

As noted in section 3.0, the primary objective is to evaluate response to anti-angiogenesis therapy using PSMA-based PET. Other endpoints such as qualitative objective response based on RECIST 1.1 and quantitative CT-based tumor size and SUV parameters will also be evaluated. The secondary objectives are 1) to measure therapy response of patient-derived uVESSEL models using multiple endpoints such as vessel sprouting, PSMA expression and cell death and 2) to evaluate the predictive power and validate the uVESSEL model for clinical outcomes.

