IND	Investigational New Drug
kg	kilogram
MBq	megabecquerel
mCi	millicurie
mGy	milligray
MicroC ³	microfluidic-cis-co-culture
mL	milliliter
mmol	millimole
mRCC	Metastatic Renal Cell Carcinoma
PACS	Picture Archiving and Communication System
PET	Positron Emission Tomography
PI	Principal Investigator
PSMA	Prostate-specific membrane antigen
RCC	Renal Cell Carcinoma
REM	Roentgen Equivalent Mammal
RF	Radio frequency
RPF	Radiopharmaceutical Production Facility
SAE	Serious Adverse Event
UP	Unanticipated Problem
UW	University of Wisconsin
UWHC	University of Wisconsin Hospital and Clinics

STATEMENT OF COMPLIANCE

The signature below constitutes the approval of this protocol and the attachments, and provides the necessary assurances that this trial will be conducted according to all stipulations of the protocol, including all statements regarding confidentiality, and according to local legal and regulatory requirements and applicable US federal regulations and ICH guidelines.

I agree to ensure that all staff members involved in this study are informed about their obligations in meeting the above commitments.

Principal Investigator: [name]

Signed:

Date:

[name].
Department of Radiology, Nuclear Medicine Section
University of Wisconsin School of Medicine and Public Health
University of Wisconsin Carbone Comprehensive Cancer Center

PROTOCOL SUMMARY

Title	Functional Microscale Organotypic Assays to Predict Patient Response to Anti-Angiogenesis Therapies.
IND Sponsor-Investigator	[name]
Co-Investigators	[name] E. [name] [name]
Participating Site	University of Wisconsin-Madison
Patient Population	Patients diagnosed with metastatic clear cell RCC that are surgical candidates
Accrual Objective	This research will enroll 15 subjects
Study Design	Phase 2, single-center, open-label study
Study Duration	The estimated accrual period is over 3 years
Primary Objective	The primary objective of this research is to evaluate response to systemic therapy, including anti-angiogenesis and/or immune-based therapies, via ¹⁸ F-DCFPyL PSMA-based PET/CT in patients with metastatic renal cell carcinoma and to compare qualitatively with conventional imaging response criteria (RECIST 1.1) and histopathological endpoints including isolation, enumeration and staining of Circulating Tumor Cells (CTC).
Secondary Objectives	1. Measure therapy response of patient specific uVESSEL model 2. Evaluate the predictive power and validate the uVESSEL model

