In addition to anti-angiogenesis agents, immunotherapy has also been shown to play an important role in the treatment of patients with metastatic RCC. Nivolumab is an anti-programmed cell death 1 (PD-1) monoclonal antibody that was approved by FDA in 2015 based on a phase III clinical trial that showed improvement in survival compared to the mTOR inhibitor everolimus in patients whose disease had developed resistance to anti-angiogenesis therapies (Motzer 2015). More recently, combination immunotherapy with nivolumab and ipilimumab, which is an anti-cytotoxic T-lymphocyte-associated protein 4 (CTLA-4) monoclonal antibody, demonstrated improvement in survival compared to sunitinib (Motzer 2018) and eventually became the preferred standard-of-care first-line treatment for patients with metastatic RCC. Finally, two additional trials that were published in March of 2019 showed that the combination of axitinib with anti-PD-1 immunotherapy (pembrolizumab and avelumab respectively) [Rini 2019; Motzer, 2019] showed superiority compared to sunitinib and are currently pending approval by FDA as first-line therapies for metastatic RCC. In this rapidly evolving field, it is unclear how the most recent studies will impact the care of these patients, however systemic therapy with anti-angiogenesis agents will continue to play an important role.

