3.0 OBJECTIVES

3.1 Primary Objective: To evaluate response to systemic therapy, including anti-angiogenesis and/or immune-based therapies, via ¹⁸F-DCFPyL PSMA-based PET/CT in patients with metastatic renal cell carcinoma and to compare qualitatively with conventional imaging response criteria (RECIST 1.1) and other histopathological endpoints including isolation, enumeration and staining of Circulating Tumor Cells (CTC).

Response of systemic immune-based and/or anti-angiogenesis therapies will be quantified using PSMA-based PET imaging using a novel agent, ¹⁸F-DCFPyL, as a non-invasive imaging biomarker of tumor neovasculature to functionally monitor renal cell cancer neovasculature in patients undergoing systemic anti-angiogenesis therapy. PSMA PET will be compared with response to anti-angiogenesis therapy using conventional imaging computed tomography(CT)-based RECIST1.1 criteria (Eisenhauer 2009) as well as histopathological endpoints (tumor vascular density, immunohistochemical staining for PSMA and neovascularization (CD105, CD31). Whole body PSMA PET/CT scans will be obtained at baseline, following adjuvant anti-angiogenic therapy and when the patient becomes refractory to treatment.

The rationale and time points for obtaining PET scans is planned with respect to the typical natural history of metastatic RCC. This project will obtain information from tumors that are responding to anti-angiogenesis therapy and those resistant to treatment.

PET1 is obtained pre-surgically to establish the baseline tumor PET and CT characteristics prior to

surgical removal of the primary renal tumor and metastatic sites (e.g. LNs). Surgery technique is not altered for this study.

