If the first line SOC systemic therapy did not include an anti-angiogenesis therapy and if this second systemic therapy includes anti-angiogenesis therapy, an additional 4th and 5th PET imaging will be obtained as PET3A and PET3B. PET3A is obtained prior to start of additional systemic therapy including anti-angiogenesis therapy, to establish a new baseline PET before this systemic therapy commences, to characterize the existing metastatic tumors and any metastatic tumors which develop between PET2B and start of this systemic therapy. PET3B is obtained at 12-16 weeks from start of this second systemic therapy including anti-angiogenesis therapy (with associated SOC conventional diagnostic chest/abdomen/pelvis CT) to evaluate mRCC tumors response to treatment.

Following recovery from surgery the patients will initiate systemic therapy as per SOC. The patients will receive systemic therapy with an antiangiogenic agent as per first-line or later SOC therapy. There are currently 4 oral antiangiogenic agents approved by FDA for the treatment of patients with metastatic RCC (pazopanib, sunitinib, cabozantinib, axitinib) and patients on this study will receive one of those 4 agents as per physician's preference.

Study procedures will include a tissue analyses as well as the use of PET/CT imaging to monitor subject's clinical response to treatment. For tissue, immune cell and CTC analyses, investigators will be working with the UWCCC Biobank staff to acquire blood samples and tissue samples donated from the kidney with primary tumor, lymph nodes, and any other metastatic site from which tissue was collected.

Subjects will be asked to complete four to six research visits that will include the administration of a PSMA PET/CT exam. There will be an initial baseline ¹⁸F-DCFPyL PSMA PET/CT (PET1) prior to nephrectomy and SOC biopsy of metastatic sites as clinically indicated, followed by a second ¹⁸F-DCFPyL PSMA PET/CT (PET2A) prior to start of systemic anti-angiogenesis and/or immune-based therapy. A third on-treatment ¹⁸F-DCFPyL PSMA PET/CT (PET2B) will be performed at 12-16 weeks from start of systemic therapy (with associated SOC diagnostic chest/abdomen/pelvis CT). If system The fourth (or sixth if there is PET3A and PET3B) ¹⁸F-DCFPyL PSMA PET/CT (PET4) will be performed at the time of disease progression as determined by conventional imaging such as CT or MRI; or two years after initiation of therapy (whichever one comes first).

Blood and Tissue Collection

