10.2 Statistical analysis

Statistical analysis will by necessity (n=15) and nature (predictive modeling of response using patient-derived ex-vivo uVESSEL responses as predictors, among others) be exploratory and descriptive including qualitative comparison between responses based on PSMA-PET and RECIST 1.1 without a formal paired test of statistical significance.

Measures of patient response to anti-angiogenics via clinical endpoint such as response based on PSMA-PET (primary endpoint) and objective response based on RECIST 1.1 and histopathological endpoints (tumor vascular density, immunohistochemical staining for PSMA and neovascularization (CD30, CD34)) will be summarized with descriptive statistics (response rate and confidence interval), and changes in these endpoints, PSMA staining from baseline to end of treatment and follow-up) will also be summarized with descriptive statistics. Measures of tumor neovascularization via PSMA-based PET/CT imaging will be summarized with descriptive statistics over time and analyzed using generalized linear mixed-effects models for longitudinal measures. Qualitative ¹⁸F-DCFPyL PSMA PET/CT imaging will be recorded in a three-point scale, and statistical analysis will be performed with the equivocal score of 1 considered as positive or negative. Histopathological endpoints will be qualitatively graded by our study pathologist on a zero to four scale with four being the highest level of immunohistochemical staining or neovascularization.

Partial responses are likely from conventional clinical imaging in mRCC patients. Standard imaging techniques define responses to therapy based on size changes of target lesions using RECIST1.1. Metastatic tumors may respond to anti-angiogenic treatment but not change substantially in size (unlike cytotoxic therapies for which RECIST was designed). To address this limitation in current imaging, we combine standard imaging with functional imaging protocols to evaluate whether angiogenesis decreases in individual metastatic lesions regardless of changes in tumor size. PSMA PET signal is used as a surrogate for changes in tumor neovasculature. These functional imaging findings will be

confirmed pathologically by evaluating angiogenesis/ PSMA expression in tumor samples and patient models. Using this approach, we will evaluate functional anti-angiogenesis responses to therapies.

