For the uVESSEL models (secondary objective 1), generalized linear mixed-effects models for longitudinal measures taken four times will be used for various endpoints with treatment (control plus four anti-angiogenics), dose (three levels each replicated three times), and plate (primary vs metastatic crossed by normal vs tumor) as the main factors. This will allow evaluation of the effects of treatment and dose and the differences between primary and metastatic samples and between normal and tumor vessels. We will also include these two models as the main factor in a combined generalized linear mixed-effects model, which will allow direct comparison of the biomimetic and the organotypic models.

Predictive modeling (secondary objective 2) will thus include the actual tumor size change (in a typical waterfall plot) and the dichotomy of disease control vs no disease control in the predictive model for tumor response in addition to the dichotomy of responders vs. non-responders in functional studies.

Due to limited sample size (n=15) and because not all patients are treated with the same anti-angiogenic therapy, further reducing the sample size for each anti-angiogenic therapy, one cannot expect the predictive analysis to give a clear discrimination between responders and non-responders to anti-angiogenic therapies. As an alternative, we will also use clustering analysis based on k-means or Gaussian mixture models which are less sensitive to small sample sizes as in Pak (2015).

Using the clinical, pathological and imaging endpoints as dependent variables, we will develop predictive models using responses to the uVESSEL model as independent predictor variables. More specifically, we will use the objective response as a dichotomous endpoint as a dependent variable in a logistic regression model with response to the uVESSEL model as an independent predictor. This approach is equivalent to linear discriminant analysis. Although we expect about 70% of eligible patients will receive pazopanib and the rest sunitinib, we can still use the objective response as the dependent variable in logistic regression as both pazopanib and sunitinib are expected to give a similar response rate of around 30% in this patient population. In addition each patient sample will be subject to both agents in the uVESSEL model and provide response to be used as predictors in logistic regression modeling.

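### The primary PSMA-PET response rate has two stated scopes, anti-angiogenic only and any systemic therapy, and so two possible scan pairs and denominators

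*Combined protocol and SAP*

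**What the plan says.** The Protocol Summary states: "The primary objective of this research is to evaluate response to systemic therapy, including anti-angiogenesis and/or immune-based therapies". Section 3.1 opens the same way: "To evaluate response to systemic therapy, including anti-angiogenesis and/or immune-based therapies". Its later text is narrower. It describes patients on anti-angiogenesis treatment and compares PSMA PET with response to that treatment.

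Section 10.0 refers back to Section 3.0 but leaves out immune-based therapy: "the primary objective is to evaluate response to anti-angiogenesis therapy using PSMA-based PET". Section 10.2 follows the narrow scope: "Measures of patient response to anti-angiogenics via clinical endpoint such as response based on PSMA-PET (primary endpoint".

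Section 3.1 also sets the scans. PET2A and PET2B bracket the first 12-16 weeks of first-line therapy of either class. PET3A and PET3B do the same for a later line, but only if the first line had no anti-angiogenic agent and the later line has one.

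The documents differ on which therapies patients will receive:
- Section 2.0 says of an immunotherapy combination that it "eventually became the preferred standard-of-care first-line treatment for patients with metastatic RCC".
- Section 4.0 requires only that an anti-angiogenic regimen be possible.
- Section 5.0, after listing four oral anti-angiogenic drugs, says "patients on this study will receive one of those 4 agents as per physician's preference", at first or later line.
- Section 10.2, on the uVESSEL regression, says "Although we expect about 70% of eligible patients will receive pazopanib and the rest sunitinib".

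**The concern.** A response rate needs a defined numerator and denominator. Here two stated objectives lead to different ones for any patient who starts on immune-only therapy. Section 10.2 does not settle the matter: it speaks of change from baseline, while the schedule contains PET1, PET2A and PET3A, each described as a baseline. If the choice is left open until the scans have been read, it can be made with the results in view. With 15 patients, moving a few of them could change the reported rate noticeably.

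The ambiguity also reaches a secondary analysis. Section 3.2.2 uses PSMA-PET response as the outcome of a logistic model meant to separate responders from non-responders to anti-angiogenic therapy. If an immune-only PET2 result served as that outcome, the assay's response to anti-angiogenic drugs would be fitted to the effect of a different class of treatment.

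**Working it through.** **Step 1. Which scans count under each scope.** Applying the scan rules of Sections 3.1 and 5.0:

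| Patient's course | Wide scope (Summary, opening of 3.1) | Narrow scope (10.0, 10.2) |
|---|---|---|
| First line contains an anti-angiogenic agent, alone or in combination | PET2A to PET2B | PET2A to PET2B |
| Immune-only first line, anti-angiogenic agent later | PET2A to PET2B | PET3A to PET3B |
| Immune-only first line, no anti-angiogenic agent later | PET2A to PET2B | none |
| Locally advanced, metastases never identified | none | none |

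The scopes agree in the first and last rows. In the second row the patient stays in the denominator but the scan pair changes. In the third row the denominator changes. The last row follows from Section 5.0, which gives locally advanced patients no PET2A until metastases are found. Section 4.0 makes such patients eligible, so the wide scope does not guarantee 15 evaluable patients either.

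**Step 2. Reproduce the plan's precision (Section 10.1, n = 15).**
- Worst-case 95% Wald half-width: 1.96 × √(0.25/15) = 0.253. Full width: 2 × 0.253 = 0.506.
- Standard error factor for a mean: 1/√15 = 0.258.

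Both figures reproduce with all 15 patients evaluable. However, 0.253 is a half-width, and the plan calls it a width. No usual interval has a worst-case full width of 0.253 at n = 15: the largest full width is 0.521 for Clopper-Pearson and 0.451 for Wilson.

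**Step 3. Precision with fewer evaluable patients.** Let m be the number with the relevant scan pair. The documents give no value for m, so these are illustrations, using 1.96 × √(0.25/m) and 1/√m:

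| m | Half-width | Full width | Standard error factor |
|---|---|---|---|
| 15 | 0.253 | 0.506 | 0.258 |
| 10 | 0.310 | 0.620 | 0.316 |
| 8 | 0.346 | 0.693 | 0.354 |
| 5 | 0.438 | 0.877 | 0.447 |

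**The case against.** The strongest reply is that the study is about anti-angiogenic response throughout. The title, the tracer as a marker of neovasculature, the uVESSEL validation, the condition for PET3A/PET3B and much of Section 3.1 all point that way. On that view Section 10 matches the intent and only the opening sentence of 3.1 is loose. This stands in part. The conflict also lies within 3.1, and a reader might infer that Section 10 must simply be rewritten to the wide scope. The documents do not support that; which estimate is primary is the sponsor's choice. The reply does not remove the two stated scopes or supply a scan pair.

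Second, Section 5.0 says patients will receive an anti-angiogenic agent at first or later line. If that held for everyone, the third row of the table would be empty. Sections 3.1 and 4.0, however, treat such exposure as conditional, and the second row would still have two candidate scan pairs. Section 2.0 also expects anti-angiogenic agents to stay important and describes combinations with immunotherapy; patients on those fall in the first row, where there is no conflict. The affected group may therefore be small.

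Third, the analysis is exploratory, without a formal paired test, and the sample size rests on feasibility. That stands, and it limits the consequence to the meaning and precision of the primary estimate.

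**Conclusion.** The point holds as an inconsistency in current text. The primary response rate has two stated scopes, and for patients who start on immune-only therapy these give different scan pairs and possibly different denominators. No alpha, power or decision rule is affected.

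The size cannot be computed. The half-widths of 0.310, 0.346 and 0.438 rest on assumed counts of 10, 8 and 5 evaluable patients.

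Four stronger inferences are not supported:
- That immune-first patients would be counted twice. Sections 10.1 and 10.2 work with 15 patients and a response rate; nothing there counts treatment courses.
- That the objective was widened by amendment and Section 10 left behind. The documents provided do not show that history.
- That the pazopanib/sunitinib premise governs the primary endpoint. It justifies pooling in the uVESSEL regression, which is secondary.
- That scope alone undermines the precision statement. As worded, a width below 0.253 fails even with all 15 patients, and neither scope guarantees 15.

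**What to change.** Before data are seen:

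1. State one scope, scan pair and analysis set for the primary response rate, with one result per patient, in the same terms in the Protocol Summary, 3.1, 10.0 and 10.2.
2. Report two estimates, each with its own n and 95% interval: (a) PSMA-PET response from PET2A to PET2B on first-line therapy of any class, also shown by regimen class; (b) anti-angiogenic response, from the PET2 pair if first line contains such an agent and otherwise from the PET3 pair. The sponsor names which is primary.
3. Use (b) as the outcome in the Section 3.2.2 model of response to anti-angiogenic therapy.
4. Replace the premise in 10.2 that all patients receive pazopanib or sunitinib, and reconcile Sections 2.0, 3.1, 5.0 and 10.2 on which therapies patients receive.
5. In the Summary and 10.1, say that the precision applies only if all 15 patients have the relevant scan pair, and label 0.253 as a half-width.

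The cost is analysis wording. No scan, visit or patient is added. The downside is that the stated precision becomes less favourable.

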10.1 Sample size justification

A total of 15 patients will be recruited into this clinical study. This is based on the feasibility and availability of suitable patients over the funding period with approximately five patients per year. With 15 patients, the width of a 95% confidence interval for the probability of qualitative response based on PSMA-PET and objective response based on RECIST 1.1 will be less than 0.253 and the mean of quantitative endpoints such as CT-based tumor size and SUV parameters will have standard error that is 0.258 times the sample standard deviation.

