Inclusion Criteria	
 Patients diagnosed with locally advanced (\geqcT3) or metastatic clear cell RCC, as proven by biopsy. Adults, 18 years of age or older. Surgical candidates who have clinical indication for nephrectomy and standard of care biopsy of metastatic disease followed by possible standard of care systemic anti-angiogenesis based treatment regimen Have consented to participate in the UWCCC Biobank.
Exclusion Criteria	
 Patients who have received prior RCC systemic therapies Prior history of prostate cancer Prior history of any other malignancy within the last 2 years, other than skin basal cell or cutaneous superficial squamous cell carcinoma that has not metastasized and superficial bladder cancer Unable to lie flat during or tolerate PET/CT Serum creatinine $>$ 2 time the upper limit of normal
Treatment Description	¹⁸ F-DCFPyL whole body PET/CT scan administered at the following timepoints: 1) Prior to scheduled nephrectomy 2) After completion of systemic antiangiogenesis and/or immune-based therapy 3) When patient is refractory to treatment
Study Procedures	
 ¹⁸F-DCFPyL whole body PET/CT scan Review of relevant imaging and medical record information
Statistical Considerations	A total of 15 patients will be recruited into the clinical study. This is based on the feasibility and availability of suitable patients over the funding period with

	approximately five patients per year. With 15 patients, the mean of quantitative endpoints such as tumor size and SUV parameters will have standard error that is 0.258 times the sample standard deviation, and the width of a 95% confidence interval for the probability of binary qualitative endpoints such as objective response will be less than 0.253.
--	---

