3.2.3 Evaluate the predictive power and validate in-vitro immune therapy models

At the moment we are expanding our uVESSEL patient-specific organotypic models (Fig. 2) to contain more cell types from the tumor microenvironment (cancer epithelial, endothelial, immune, stromal) in similar proportions as found *in vivo*.

Patient tissue can be disaggregated, specific cell types isolated and placed in the uVESSEL model (Bischel 2014) (Jimenez-Torres et al 2019). Tumor spheroids can be created from a mixture of tumor epithelial cells and immune cells, to mimic tumor-infiltrating leukocytes, embedded in a hydrogel matrix (Sung 2014). Tumor spheroids model solid tumors and replicate the hypoxia and

[figure not shown]

Fig. 2. A) Left: model scheme showing a tumor spheroid flanked by 2 endothelial lumens. Right: a 4-microdevice array. Confocal images of B) a tumor spheroid (blue) and immune cells (green). C) tumor organoid (green) with hypoxic core (red). D) lateral endothelial lumen.

nutrient starvation observed *in vivo* in RCC (Fig. 2). Hypoxia influences the microenvironment by significantly suppressing the anti-tumor response by increasing regulatory and immunosuppressive immune cell phenotypes and reducing cytotoxic lymphocyte functions (Noman 2015). Likewise, the uVESSEL model allows for the creation of lumen structures within a hydrogel matrix that can be lined with endothelial cells to form microvessel structures, mimicking the highly vascularized nature of RCC (Jimenez-Torres 2019). Thus, we can create a carefully controlled model tumor microenvironment made entirely of primary cells all from the same patient (Fig. 2) that can be treated with various immune checkpoint inhibitors, TKI's or combinations thereof with readouts examining tumor growth, immune cell phenotype and function and angiogenesis. Our functional endpoints include spheroid size variation/viability, as well as the angiogenic sprouting endpoint already developed for TKI predictive value. Both outputs can be expressed as a dichotomous endpoint of responders/non-responders for the validation of uVESSEL performance with patient response as observed in PET/CT.

4.0 RESEARCH DESIGN AND METHODS:

Study Design: This study is designed as a single cohort study without randomization or stratification.

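### The stated 95% CI width of less than 0.253 for the response rates is a half-width; the full width at n = 15 is up to about 0.51

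*Combined protocol and SAP*

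**What the plan says.** Section 4.0 describes a single cohort, and section 10.1 sets its size: "A total of 15 patients will be recruited into this clinical study". The reason given is feasibility and patient availability, at about five patients a year. There is no power calculation.

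The plan then gives two precision figures. For quantitative endpoints the mean will have a "standard error that is 0.258 times the sample standard deviation". For binary endpoints the sentence begins "With 15 patients, the width of a 95% confidence interval for the probability of" and continues "qualitative response based on PSMA-PET and objective response based on RECIST 1.1 will be less than 0.253". The Protocol Summary (Statistical Considerations) makes the same claim more generally: "the width of a 95% confidence interval for the probability of binary qualitative endpoints such as objective response will be less than 0.253".

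Section 10.2 names response based on PSMA-PET as the primary endpoint. This and RECIST 1.1 response are to be "summarized with descriptive statistics (response rate and confidence interval"). It does not say which interval will be used.

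**The concern.** The width of an interval is its upper limit minus its lower limit. A 95% interval only a quarter of the probability scale wide is implausibly narrow for a proportion from 15 patients unless the rate is close to 0 or 1. The figure 0.253 looks like the usual margin of error at a rate of 50%, which is half the width.

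In a study with no hypothesis test and no decision rule, the precision statement is all that tells a reader what 15 patients can show about the primary endpoint. If it is wrong by a factor of two, anyone approving or funding the study is shown the precision of a much larger one.

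**Working it through.** **Inputs.** n = 15 and 95% confidence (section 10.1), so z = 1.96. The stated bound is 0.253 (section 10.1 and Protocol Summary). For illustration only, section 10.2 says that "both pazopanib and sunitinib are expected to give a similar response rate of around 30% in this patient population".

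**Step 1: confirm n from the companion figure.** 1/√15 = 0.2582, which matches the stated 0.258. So n = 15 is the input used.

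**Step 2: reproduce 0.253.** The normal-approximation (Wald) half-width is z × √(p(1 − p)/n), which is largest at p = 0.5:

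1.96 × √(0.25/15) = 0.2530.

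This matches the stated figure to three decimals, as the distance from the estimate to one limit.

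**Step 3: full width.** 2 × 0.2530 = 0.506. At p = 0.3 the half-width is 1.96 × √(0.21/15) = 0.232 and the full width is 0.464.

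**Step 4: full widths for counts that can be observed.** Limits are truncated to lie between 0 and 1. Widths for 8 to 15 responders mirror those for 7 to 0.

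| Responders of 15 | Wald | Wilson | Clopper-Pearson |
|---|---|---|---|
| 0 | 0.000 | 0.204 | 0.218 |
| 1 | 0.193 | 0.286 | 0.318 |
| 2 | 0.305 | 0.341 | 0.388 |
| 3 | 0.402 | 0.381 | 0.438 |
| 4 | 0.448 | 0.411 | 0.473 |
| 5 | 0.477 | 0.431 | 0.498 |
| 6 | 0.496 | 0.444 | 0.514 |
| 7 | 0.505 | 0.451 | 0.521 |

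From 2 to 13 responders every entry exceeds 0.253. At 1 or 14 responders only the Wald interval falls below it. Only 0 and 15 responders satisfy the bound by all three methods. Two other methods do not help: the maximum is 0.451 for Agresti-Coull and 0.467 for Jeffreys.

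For example, 7 of 15 gives 0.214 to 0.719 by Wald and 0.213 to 0.734 by Clopper-Pearson.

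**Step 5: when would the statement be true?** For a full Wald width of 0.253 at n = 15, the rate must be about 0.067 or lower, or 0.933 or higher. At a true rate of 30%, the chance of 0 or 1 responders is 0.7¹⁵ + 15 × 0.3 × 0.7¹⁴ = 0.0047 + 0.0305 = 0.035. The bound would therefore fail about 96% of the time.

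**Step 6: sample size that would deliver it.** n = (2 × 1.96)² × p(1 − p)/0.253². At p = 0.5 this is 60.0. At p = 0.3 it is 50.4, so 51 patients. These are 4.0 and 3.4 times the planned 15.

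**The case against.** The arithmetic is not in dispute; the weight to give it is. The sample size was not derived from 0.253 but from feasibility. Section 10.2 calls the analysis exploratory and descriptive, and it acknowledges the limits of n = 15. No hypothesis, stopping rule or success threshold uses the figure. The intervals finally reported will be computed from the data, so the mislabel cannot carry into them. A statistician reading the sentence would probably guess that a half-width was meant.

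All of this stands, and it limits the consequence: the design, the sample size and the reported intervals are unaffected. It does not make the sentence true, and readers who are not statisticians will not make the correction for themselves.

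Two points on wording also stand. First, the 30% rate in section 10.2 concerns objective response to two named drugs. It is not a PSMA-PET response rate, and the plan also allows immune-based first-line therapy, so widths at 30% are illustrative. Second, Wald figures should not be mixed with another method's name. A maximum of about 0.51 would be false for Clopper-Pearson (0.521), and it is not the Wilson maximum (0.451). Both of those intervals are generally asymmetric about the estimate, so a half-width describes them poorly.

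**Conclusion.** The statement is wrong as written in both places. The figure of 0.253 is a correctly computed Wald half-width presented as a width. The worst-case full width at n = 15 is 0.506 by Wald, exactly twice the stated bound. By the other methods checked it is 0.451 to 0.521, or about 1.8 to 2.1 times the bound.

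The factor of two needs no assumption beyond n = 15 and 95% confidence. The widths also assume that all 15 patients are evaluable for response. With fewer the interval is wider: at 10 evaluable patients the worst-case Wald full width is 0.620.

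The error changes no test and no sample size. It should still be corrected, because it is the only precision claim for the primary endpoint.

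**What to change.** Correct the sentence in section 10.1 and its counterpart in the Protocol Summary. Name the interval in section 10.2 and use that method's figures throughout. Any one of these is enough:

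- **Clopper-Pearson:** with 15 evaluable patients, the full width of the exact 95% interval is at most 0.52, and about 0.47 to 0.50 with 4 or 5 responders.
- **Wilson:** the full width is at most 0.45, and about 0.41 to 0.43 with 4 or 5 responders.
- **Normal approximation, if kept:** the half-width is at most about 0.253 and the full width at most about 0.51, or about 0.46 at a 30% rate.

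Either of the first two is preferable at this sample size. With 0 responders the Wald interval has zero width, and with 1 to 3 it has to be cut off at zero.

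The cost is two corrected sentences and one named method. The stated precision becomes less favourable. The number of patients, the procedures and the analysis do not change, and the figure of 0.258 for the standard error stays as it is.
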